### E. Decitabine induced myeloid differentiation

To determine whether decitabine induces multilineage differentiation, or myeloid biased differentiation, we will identify cases where discordant morphologic blast clearance occurs without mutation clearance (Figure 4). We will flow sort differentiated peripheral blood monocytes, neutrophils, T cells, B cells, and NK cells and evaluate each population for the presence of AML-associated mutations. We compare results of samples sorted from Day 0, C1D28, C2D28, and C3D28, as appropriate.

## **F. Correlation of the rate and depth of mutation clearance with survival**

We will assess tumor burden by allele frequency of patient-specific mutations in bone marrow or peripheral blood samples collected pre study, C1D28, C2D28 and C3D28 as well as at regular intervals after transplant. The velocity and depth of tumor response will be correlated to:

- Achievement of clinical CR,
- Time to best response,
- Mutational status,
- Time to disease progression

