### 1.2 Study Rationale

Among patients with complex or monosomy karyotypes, nearly 60% carry *TP53* mutations; whereas nearly all patients with *TP53* mutations have complex or monosomy karyotypes, and these karyotypes almost always involve deletion of chromosome 5q, chromosome 7, chromosome 12, or chromosome 17p. Patients with *TP53* mutations tend to be older (median age 61 vs 54 years), have worse response to conventional chemotherapy (complete remission rate: 28% vs 50%), shorter event free survival (3-year EFS: 1% vs 13%), and overall survival (3-year OS: 3% vs 28%).

We correlated response to decitabine with mutation status in 99 patients with AML or MDS. We observed response (complete remission (CR), complete remission with incomplete blood count recovery (CRi), or marrow complete remission (mCR) in 21/21 patients with *TP53* mutations. ( $p < 0.0001$ ). No other gene mutation was associated with

response in the 99 patients sequenced (Figure 1A).

Consistent with this, we observed mutation clearance in all 16 cases with TP53 mutations evaluated at serial time points, and that TP53 mutations were cleared more quickly and consistently than other variants (Figure 2).

Decitabine alone does not lead to a cure in the majority of responding patients. Mutation clearance is nearly always incomplete, and we could detect low levels of mutations (0.2 - 5%) in 20 of 20 patients analyzed during remission with enhanced exome sequencing. Furthermore, in all 9 patients analyzed at relapse, the relapse occurred via subclonal evolution (expansion of a subclone that carries the founding clone mutations and additional mutations, suggesting that the founding clone mutations persisted during morphologic remission).

Several clinical variables correlated with survival in this cohort: age, performance status (2 vs 0-1), and whether the patient underwent stem cell transplantation (Figure 3A). Thus, additional consolidation (e.g. hematopoietic cell transplantation) appears necessary to

achieve prolonged remissions. Importantly, in this cohort of patients who undergo decitabine induction, the presence of *TP53* mutations no longer adversely affected survival following transplantation.

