These data suggest that decitabine may have unique efficacy in patients with *TP53* mutations. In this study, we seek to determine whether decitabine therapy can improve outcomes, specifically overall survival, of this selected subset of AML patients with the poorest prognosis based on refractoriness to induction treatment and high-risk genetic mutations.

[figure not shown]

Figure 2. Consistent clearance of *TP53* mutations. A. The variant allele frequency of *TP53* mutations was consistently reduced during decitabine treatment. Twenty-one *TP53* mutations were evaluated at multiple time points in 16 patients, (e.g. cycle 2 day 28, C2D28). Variant allele frequency indicates the proportion of variant reads vs. the total number of reads at that nucleotide, and is proportional to the tumor burden. B and C. Mutation clearance of *SRSF2* and *DNMT3A* mutations. D. Summary of rate of mutation clearance. Note that during decitabine therapy, *TP53* mutations were consistently, and rapidly, cleared when compared with mutations in other genes. P value calculated with ANOVA using Tukey’s post-test correction.

[figure not shown]

Figure 3. Overall survival subgroup analysis. A. Overall survival was increased in patients treated with 10 day decitabine who underwent stem cell transplantation vs. those who did not. B. Among patients who underwent stem cell transplantation, survival was not impacted by the presence or absence of *TP53* mutations. P value calculated as Log-rank.

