#### **F. Secondary *Molecular Endpoints Analyses***

**Rate of patient specific mutation clearance** after 28, and 56 days of therapy will be determined using an Illumina based platform. We will compare the rate of mutation clearance between the patients who achieve a CR/CRi after 4 cycles and those who do not. We anticipate that we will identify between 6 and 25 exonic SNVs per case (the range obtained with >200 AML samples sequenced to date with whole genome or exome sequencing), and that the expected 95% confidence interval of the mean variant allele frequency will be  $\pm 2.56\%$  and  $\pm 1.25\%$ , respectively, if we assume an anticipated standard deviation of 3.2% within the same clone. The change of tumor burden over time and its association with clinical response will be assessed using 2-way ANOVA for repeated measurement data, followed by the ad-hoc multiple comparisons for between-group differences (e.g., responders vs. non-responders) at given time points as well as the between-time differences within each group. The resultant critical P values will also be corrected using permutation analysis for multiple testing.

The percent decrease in bone marrow methylcytosine will be calculated on day  $10 \pm 1$ . We will compare this reduction with previously published data and between the patients who achieve CR/CRi and those who do not. The correlation of peak plasma levels of decitabine with response will be assessed using 2-sample t-test or Mann-Whitney non-parametric rank-sum test as appropriate. The change of total bone marrow DNA methylcytosine from baseline and its association with both steady-state plasma drug levels and response will be assessed using 2-way ANOVA for repeated measurement data, followed by the ad-hoc multiple comparisons for between-group differences (e.g., responders vs. non-responders) and between-time

differences. Similar analyses will be performed for the correlation of expression profiles and SNP analysis with pharmacokinetic data.

The proportion of patients who achieve mutation clearance to <0.1%, after 3 cycles of decitabine, will be calculated and its 2-sided 90% confidence interval (CI) will also be provided. Using a sensitive sequencing technology such as Haloplex, the sensitivity of PB or BM for detecting residual mutation burden, as well as the *TP53* clonal burden reduction after consolidation with stem cell transplantation will be summarized using contingency tables.

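### Sections 9.1.F and 15.4.F read tumor burden from raw allele frequency with no copy-number handling and no fixed scale of change, which distorts clearance at deleted loci, mainly for single-locus measures such as TP53

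*Combined protocol and SAP*

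**What the plan says.** Section 9.1.F of the combined protocol and SAP defines the measure: "We will assess tumor burden by allele frequency of patient-specific mutations in bone marrow or peripheral blood samples". The speed and depth of its fall are then related to clinical CR, time to best response, mutational status and time to progression. The premise is in the Figure 2 legend of Section 1.2, which says that variant allele frequency "is proportional to the tumor burden", without qualification.

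Section 15.4.F gives the analysis: "The change of tumor burden over time and its association with clinical response will be assessed using 2-way ANOVA for repeated measurement data", followed by comparisons of responders with non-responders. It expects several variants per patient ("We anticipate that we will identify between 6 and 25 exonic SNVs per case") and sizes the precision of their mean VAF "if we assume an anticipated standard deviation of 3.2% within the same clone".

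On karyotype, Section 1.2 says that nearly all patients with TP53 "mutations have complex or monosomy karyotypes", and that "these karyotypes almost always involve deletion of chromosome 5q, chromosome 7, chromosome 12, or chromosome 17p". Section 3.1 names del17p as an example of a persistent abnormality that qualifies a patient. Cytogenetics and FISH are done on the pre-study marrow (Section 5.1.A) and on the Day 28 marrows of Cycles 1 to 3 (Section 5.1.H).

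Neither 9.1.F nor 15.4.F mentions copy number, and neither says whether clearance is measured as an absolute, percent or log change.

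**The concern.** Proportionality between VAF and the fraction of mutated cells holds at a two-copy locus with a heterozygous variant. It fails where tumor cells have lost the normal allele, because the loss also removes reads from the denominator. By the protocol's own account the trial selects patients whose leukemias usually carry such losses, and TP53 lies on 17p, one of the listed regions.

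Raw VAF therefore puts variants in deleted segments on a different, curved scale from the rest, both within a patient and between patients. If deletions are distributed unequally between responders and non-responders, part of an apparent link between clearance and outcome can be copy number. If they are not, the mixture of scales adds noise. A measure based on TP53 alone is the most exposed, because no averaging over other variants dilutes the distortion.

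**Working it through.** **The plan's own figures.** The half-width of the 95% interval for a mean VAF is 1.96 × SD/√n. With SD 3.2 points, n = 6 gives 2.56 and n = 25 gives 1.25. Both agree with Section 15.4.F.

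**Formulas.** Let T be the fraction of cells carrying the mutation. Assume that every tumor cell carries it, that normal cells have two copies, and that any deletion is present in every mutated cell.
- Two-copy heterozygous locus: VAF = T/2, so T = 2 × VAF.
- Normal allele deleted: VAF = T/(2-T), so T = 2 × VAF/(1+VAF).
- For a fall from T0 to T1, the ratio of deleted to two-copy results is 4/((2-T0)(2-T1)) for the absolute drop and (2-T1)/(2-T0) for the fold reduction.

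**Examples (values of T assumed).**
- T 70% to 10%: two-copy VAF 35.0% to 5.0%, a drop of 30.0 points. Deleted 53.8% to 5.3%, a drop of 48.6 points.
- T 90% to 20%: drops of 35.0 and 70.7 points (ratio 2.02), fold reductions of 4.5 and 7.4.
- T 20% to 2%: the absolute-drop ratio is only 1.12.
- At VAF 0.1%, T is 0.2000% (two-copy) or 0.1998% (deleted), so deletion does not move the clearance cut.

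**Effect on a mean over variants.** Suppose one of six variants is deleted at T = 0.9. Its VAF is 81.8% against 45.0% for the others, a gap of 36.8 points. The mean shifts by 36.8/6 = 6.1 points, against the planned half-width of 2.56. The between-locus SD is 36.8 × √(5/30) = 15.0 points, against the planned 3.2 and the maximum of 4.7 in Section 15.4.G. With one of 25 the shift is 36.8/25 = 1.5 points. At T = 0.2 the shifts are 0.19 and 0.04 points.

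**False-positive rates.** Simulation of 30 responders and 30 non-responders with identical cell clearance, compared by a two-sided 5% t-test on change (a simplification of the planned ANOVA; 4,000 replicates). Assumed: T0 uniform on 0.3 to 0.9, log10 fall with mean 1.0 and SD 0.4, and deletion prevalence of 60/40, 70/30 or 75/25 between the groups.
- Single locus, absolute VAF change: about 11%, 29% and 43%.
- Single locus, log-fold change: about 5 to 10%.
- Mean of six variants, absolute change: about 5 to 8% with one deleted, 6 to 14% with two deleted.
- Mean of 25 variants, absolute change, one deleted: about 5%.
- Single locus, absolute change, T0 uniform on 0.05 to 0.4: about 5 to 9%.
- Cell-fraction scale, or equal deletion prevalence in both groups: about 5%.

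**The case against.** The strongest reply is that the planned measure is not a single VAF. Section 15.4.F expects 6 to 25 variants per case and works with their mean, and a deletion alters only the variants inside it. Section 1.2 lists the four regions as alternatives and gives no share for 17p. No imbalance of deletions between response groups has a source in the documents. All of this stands, and it limits the size of the point.

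Four stronger readings are tempting, but the documents do not support them.
- A reader might infer that because most clones carry a deletion, most tracked variants are distorted. Nothing says how many fall in deleted segments.
- A reader might take twofold as the ceiling. It is the limit for fold reduction. The absolute drop already reaches 2.02 for T 90% to 20%, and its limit is near 4. Percent reduction in that same example differs only as 86% against 78%.
- A reader might set the 18.6-point gap (48.6 - 30.0) against the 10- and 15-point differences in Section 15.4.G. Those are changes between two time points within a clone, with variants as the unit: a two-sample t-test with 6 or 3 variants per time point and SD 4.7 gives 91.2% and 82.8%, matching the stated 91% and 82%. They are not differences between patients.
- A reader might extend the 11 to 43% rates to every molecular analysis. They apply to one locus, absolute change and unequal deletion. TP53 burden reduction after transplant is a single-gene measure, but 15.4.F summarises it in contingency tables, so those rates do not carry over to it directly. That TP53 clears faster than other genes is background from the prior cohort, not a planned test.

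What the reply does not remove is that the stated premise fails at some loci in the population selected, and that the plan neither corrects for it nor fixes a scale on which it would matter less.

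**Conclusion.** The point holds as a correctable weakness in the correlative analyses. Raw VAF is used as tumor burden on a proportionality that fails at deleted loci, in patients whom the protocol itself describes as nearly always carrying deletions.

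Its size depends on what is analysed. It can be material for TP53-only or single-locus measures on the absolute scale. It is modest when one or two of six variants are deleted, close to nil with one of 25, and small on log-fold change or at low tumor fraction. It is nil for the <0.1% cut. The false-positive rates rest on assumed deletion splits and clearance distributions, and the algebra on clonal variants and deletions. The primary 1-year survival analysis is untouched.

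**What to change.** In Sections 9.1.F and 15.4.F:
- State the scale of change, for example log-fold change from baseline.
- Compute tumor burden from variants outside the regions altered on the karyotype and FISH. Alternatively, where copy state is known, convert each VAF to mutated-cell fraction before averaging: 2 × VAF at two-copy heterozygous loci and 2 × VAF/(1+VAF) at one-copy loci.
- Report raw VAF as a sensitivity analysis.
- For TP53-only summaries, report copy state at 17p alongside the result.

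The cost is a few sentences in the plan and a little extra analysis. No new samples, visits or patients are needed, since cytogenetics and FISH are already collected. The downside is that variants with uncertain copy state drop out of the main analysis. These include any with copy-neutral loss of the normal allele, which the documents do not mention and which karyotype and FISH may not show.

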### 2.2 Secondary Endpoints

1. To determine the proportion of responding *TP53* mutated patients (CR, CRi) compared to historical controls (10%-15%)
2. To determine the time to stem cell transplant among subjects who are suitable candidates for transplant and have an identified donor.
3. To correlate response and survival with clinical parameters:
  - morphologically evident disease (>5% blasts by cytomorphology) versus molecularly detected disease at the time of enrollment (disease detected with flow cytometry, cytogenetic, or mutational analysis if ≤ 5% blasts by cytomorphology);
  - *de novo AML versus secondary AML versus treatment-related AML*,
  - presence *versus* absence of cytogenetic abnormalities in addition to *TP53* mutations.
4. To determine the median time to leukemia relapse (TTLR) in non-transplant patients treated with decitabine compared to historical control (6-8 months).
5. To determine the 2-year event free survival after transplant in patients treated with decitabine compared to historical control (18-22%).
6. To determine the median and average number of hospital days during Cycles 1 and 2.

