### 2.3 Exploratory Molecular Endpoints

1. To determine the proportion of patients who achieve mutation clearance to <0.1%, after 3 cycles of decitabine.
2. To determine whether PB or BM has the greater sensitivity for detecting residual mutation burden using a sensitive sequencing technology such as Haloplex.
3. To determine *TP53* clonal burden reduction after consolidation with stem cell transplantation using a sensitive sequencing technology such as Haloplex.
4. To determine whether decitabine induces consistent methylation signatures using whole genome bisulfite sequencing.
5. To determine whether decitabine induces consistent expression signatures using RNA sequencing, and whether these correlate with methylation signatures.

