## 3.0 PATIENT SELECTION

### 3.1 Inclusion Criteria

1. *TP53* mutant AML. The presence of a *TP53* mutation should be determined by Genoptix (or institutional preferred equivalent assay). Detection of a *TP53* mutation at the time of initial diagnosis is sufficient for enrollment at the time of relapsed/refractory disease. Detection of a *TP53* mutation in either the peripheral blood or bone marrow is adequate for enrollment. (Refer to Appendix B for definition of *TP53* mutant AML.) Alternatively, patients who have not had *TP53* mutation analysis performed, but who have > 20% *TP53* positive cells by immunohistochemistry detected on a bone marrow aspirate may also be enrolled, provided that mutation analysis is requested at the time of enrollment.
2. Relapsed/refractory AML following 7+3 (or similar cytarabine containing induction chemotherapy for AML) disease detected by one of the following methods:
  - Bone marrow blasts > 5%, or
  - Hematologics flow cytometry assay (threshold > 0.5%) (alternative equivalent assay may be substituted), or
  - Persistent cytogenetic abnormality (e.g. del5, del17p, etc) by FISH or conventional karyotyping, or
  - Persistent *TP53* mutation (at least 5 variant reads with at least 50x coverage) determined by Genoptix (or institutional preferred equivalent assay).

Patients with > 10% blasts on a Day +14 bone marrow biopsy following 7+3 may either be enrolled or may be treated with a course of standard re-induction (e.g. 5+2 or similar) and then re-evaluated for response. Eligible patients will meet any of the above criteria on a subsequent biopsy.

3. Bone marrow and organ function as defined below:
  - Peripheral white blood cell count < 50,000/mcl (patients may receive hydroxyurea as necessary for cytoreduction),
  - Total bilirubin < 1.5 x upper limit of normal,
  - AST and ALT < 2.5 x upper limit of normal,
  - Serum creatinine < 2.0 x upper limit of normal, and,
4. At least 18 years of age.
5. Women of childbearing potential and men must agree to use adequate contraception (hormonal or barrier method of birth control, abstinence) prior to study entry and for the duration of study participation. Should a woman become pregnant or suspect she is pregnant while participating in this study, she must inform her treating physician immediately
6. Ability to understand and willingness to sign an IRB approved written informed consent document (or that of legally authorized representative, if applicable)

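### The analyses of mutation clearance against response and progression (9.1.F, 15.4.F) make no allowance for pre-study allele frequency and leave velocity and depth undefined, so entry burden can create an association in either direction.

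*Combined protocol and SAP*

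**What the plan says.** **Sampling.** Section 9.1.F collects a baseline value: "We will assess tumor burden by allele frequency of patient-specific mutations in bone marrow or peripheral blood samples collected pre study", then at the end of cycles 1, 2 and 3 and after transplant.

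**Correlation.** The same section says "The velocity and depth of tumor response will be correlated to" four items: clinical CR, time to best response, mutational status and time to progression. It gives no formula for velocity or depth, and no model, covariate or stratum.

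**Model.** Section 15.4.F says "The change of tumor burden over time and its association with clinical response will be assessed using 2-way ANOVA for repeated measurement data", with follow-up contrasts of responders and non-responders at given time points. It also says "We will compare the rate of mutation clearance between the patients who achieve a CR/CRi after 4 cycles and those who do not". No baseline term is named, and no model is given for time to progression.

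**Threshold endpoint.** Section 2.3 item 1 reads "To determine the proportion of patients who achieve mutation clearance to <0.1%, after 3 cycles of decitabine". Section 15.4.F reports this as a proportion with a 90% CI.

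**Entry burden.** Section 3.1 item 2 admits more than 5% marrow blasts, flow cytometry above 0.5%, a persistent cytogenetic abnormality, or a persistent *TP53* mutation with "at least 5 variant reads with at least 50x coverage". Section 2.2 item 3 treats "molecularly detected disease at the time of enrollment (disease detected with flow cytometry, cytogenetic, or mutational analysis if ≤ 5% blasts by cytomorphology") as a category to set against morphologically evident disease. That split is applied to clinical response and survival only.

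**The concern.** A patient who enters with a low VAF and one who enters with overt leukemia may lose the same fraction of the clone and still differ greatly in end level and in absolute fall.

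The outcomes are also tied to entry burden by the definitions in Section 12.1. CR needs fewer than 5% marrow blasts, which some molecular-only entrants already meet before treatment. PD in a patient enrolled below 20% blasts needs more than 20% blasts as well as a rise of over 50% from baseline.

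Entry burden can thus act on both sides of the correlation. The report could state that clearance predicts CR or later progression, or the reverse, when the drug removed the same fraction of the clone in everyone.

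**Working it through.** **1. The scale the plan appears to use.** The molecular figures in 15.4.F and 15.4.G reproduce on untransformed VAF points.
- CI half-width, 1.96 × SD/√n with SD 3.2: 1.96 × 3.2/√6 = 2.56 and 1.96 × 3.2/√25 = 1.25, both as stated.
- Power of a two-sided two-sample t-test at α = 0.05, with noncentrality d/(SD√(2/n)) and 2n − 2 df:
  - SD 3.2: 10 points with 6 variants gives 99.8% (stated >99%); 15 points with 3 variants gives 98.6% (stated >98%).
  - SD 4.7: 91.2% and 82.8% (stated 91% and 82%).

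This supports an analysis on the raw VAF scale, but the plan does not say so outright.

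**2. The range at entry.** Five variant reads are 5/50 = 10% at the minimum coverage, 5/500 = 1% at 500x and 5/1000 = 0.5% at 1000x. The 10% VAF definition in Appendix B sets no floor at study entry, because Section 3.1 item 1 accepts a mutation found at initial diagnosis.

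**3. Direction depends on the metric.**
- *End level.* The fold fall needed to reach 0.1% is 40/0.1 = 400 from a VAF of 40%, 10/0.1 = 100 from 10%, 1/0.1 = 10 from 1%, and 0.5/0.1 = 5 from 0.5%. Low-burden entrants look deep.
- *Absolute drop or slope.* The largest possible drop is 40 points from 40% but 0.5 points from 0.5%. Low-burden entrants look shallow or slow.
- *Log-ratio to baseline.* There is no built-in direction.

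**4. False association with CR.** Assumptions, none from the documents except n = 60: log10 fall with mean 1.5 and SD 0.5, unrelated to CR; overt entrants log-uniform between 10% and 50% VAF; Mann-Whitney test at 5%; 1,200 to 3,000 replicates per setting (Monte Carlo SE up to √(0.38 × 0.62/1200) = 1.4 points).

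| Molecular-only share | Their entry VAF | CR, molecular-only vs overt | On-treatment VAF | Absolute drop | Log-ratio |
|---|---|---|---|---|---|
| 30% | 0.2–5% | 70% vs 40% | 30% | 38% | 5% |
| 30% | 0.2–5% | 80% vs 30% | 71% | 81% | about 5% |
| 10% | 0.2–5% | 70% vs 40% | 11% | – | 5% |
| 30% | 1–30% | 70% vs 40% | 14% | – | – |
| 30% | 5–40% | 70% vs 40% | 6% | 11% | – |
| 30% | 0.2–5% | 50% vs 40% | 9% | – | – |

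(A dash means no figure is given for that setting.) In the first setting, a raw-scale group-by-time contrast, which is closer to the planned ANOVA, was falsely significant in 34% of trials. With equal CR rates every metric returned to about 5%, so entry burden is the cause.

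**5. False association with time to progression.** Assumptions: n = 60; 10–40% of patients enter at VAF 0.5–5% and the rest at 10–45%; log10 fall with mean 1.0 or 1.5 and SD 0.7 in all patients; progression time depends only on entry burden (mean 12 vs 6 months); 2,000 runs per setting; Spearman correlation.
- Lowest VAF: rejects in 8–29% of runs, with deeper clearance tied to later progression (ρ 0.06 to 0.18).
- Absolute drop or slope: rejects in 8–41%, with the opposite sign (ρ −0.07 to −0.22).
- Log fold-reduction: about 5%, ρ about 0.
- Lowest VAF adjusted for baseline rank: 6–7%.

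**The case against.** **Baseline is not ignored.** The pre-study VAF is collected and 15.4.F analyses change over time. This stands as far as it goes, but repeated measures on raw VAF is not baseline adjustment: the change is bounded by the starting value.

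**A fixed direction.** A reader might infer that low-burden patients will pass as deep molecular responders. The documents do not support that. Depth is undefined, and on the absolute-change scale that the power figures suggest, the artifact runs the other way.

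**The 0.1% threshold.** A reader might also take this endpoint to be part of the 9.1.F correlations. It is not: 2.3 and 15.4.F present it as a stand-alone proportion. Its mix of entry burdens affects how it reads, not whether a correlation is valid.

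**The low-VAF input.** Section 1.2 says "we could detect low levels of mutations (0.2 - 5%) in 20 of 20 patients analyzed during remission", but that describes remission in the earlier decitabine cohort, not entry after 7+3. Section 9.1.D reports that blast clearance precedes mutation clearance, so 5% blasts or fewer can coexist with a substantial VAF. This objection stands. With entry VAF of 5–40% in molecular-only patients, the false-positive rates fell to 6% and 11%.

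**Importance.** These are correlative analyses in an exploratory setting. Because the pre-study VAF is collected, adjustment remains possible at the analysis stage. This also stands, and it limits the weight of the point.

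**Conclusion.** The point holds as a gap in specification with a real mechanism. Velocity and depth are undefined, no pre-study VAF term is planned, eligibility allows widely different burdens, and the CR and PD definitions depend on entry blasts. A spurious association can follow, and its sign depends on the metric chosen.

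Its size is illustrative. False-positive rates for unadjusted metrics against CR ran from about 5% to 40% with CR rates of 70% versus 40% or closer, and up to 81% with 80% versus 30%. They rest on an assumed molecular-only share, entry VAF, CR gap and common fractional clearance, and mostly on rank tests rather than the planned ANOVA. A claim that the analysis will mislead by a particular amount would go beyond the documents.

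The 1-year OS analysis and its interim futility rule do not use these results. This is a minor improvement.

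**What to change.** - In 9.1.F and 15.4.F, define depth as log10(VAF at sample / pre-study VAF), and velocity as the change in that quantity over a stated interval.
- Run the 15.4.F ANOVA and the 9.1.F correlations on that scale, with log10 pre-study VAF as a covariate.
- State the assay detection limit and treat values below it as left-censored.
- Exclude patients with no measurable pre-study VAF from the ratio analysis, and report how many there are.
- Report the proportion below 0.1% overall and, as a descriptive addition, by pre-study VAF or by >5% versus ≤5% blasts at entry. Pre-study VAF is the more direct split, since blast count is an imperfect proxy for it.

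**Cost.** Analysis-plan wording, one model degree of freedom, a detection limit that the plan does not now state, and the loss from the ratio analysis of patients who enter on flow cytometry or karyotype without a measurable VAF, probably few. No new samples are needed.
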